### 5.3.3 Supportive Care for the control arm

Patients who are randomized to the control arm will receive supportive care or treatment designated by their treating physicians

## 6 Patient Evaluation

### 6.1 Study Calendar

Treatment Protocol Days	Pre-treatment (baseline)	Day 0	1	2	3	4	5	6	7	14	21	28
Visit window										+2	+2	+2
Informed consent	X											
Randomization		X										
Demographics %	X											
History *b	X	X	X	X	X	X	X	X	X b	X b	X b	X b
Physical Exam	X	X	X	X	X	X	X	X	X b	X b	X b	X b
Vital signs a	X	X	X	X	X	X	X	X	X b	X b	X b	X b
Weight (kg) and height	X											
MSC Infusion for MSC arm		X			X #	X #	X #					
APACHE II Score	X											
SOFA/CURB-65 Score	X											X c
ARDS Assessment c	X	X	X	X	X	X	X	X	X	X	X	X
6-point Ordinal Scale	X	X	X	X	X	X	X	X	X b	X b	X b	X b
SAR-CoV-2 PCR	X											
CBC w/ diff	X	X	X	X	X	X	X	X	X	X d	X d	X d
CMP	X	X	X	X	X	X	X	X	X	X d	X d	X d
Coagulation Studies @	X	X e	X e		X e		X e		X e	X e	X e	X e
LDH	X	X e	X e		X e		X e		X e	X e	X e	X e
C-Reactive Protein (CRP)	X	X e	X e		X e		X e		X e	X e	X e	X e
Research Cytokine Profile and labs		X &	X		X		X		X	X d		X d
Chest X-Ray/ Computerized Tomography (CT scan) e	X	X e	X e		X e		X e		X e	X	X	X
Pregnancy test (if CBP)	X											
Adverse Events		X	X	X	X	X	X	X	X	X	X	X

a - vital signs to include HR, BP, Temp (max temp for the day), RR, Oxygen Saturation (O2 sat)

b - Should be done **daily** if patient still hospitalized

c - if remains in the ICU and ABG available per SOC. ARDS severity requires PaO2 to calculate

d- only required if patient remains hospitalized at this time point

e- done per SOC; not mandated by study. Date will be collected from medical record at these timepoints if available

\*- includes concurrent medications

%- includes age, gender and ethnicity

# - if inadequate response to initial infusion, a second infusion may be given within 3-5 days following the first infusion; no more than 2 infusions will be administered

@ - coagulation studies = PT/aPTT, d-dimer, fibrinogen

& - collected pre-infusion and 3-4 hours post-infusion

## 7 Evaluations

For patients randomized to the control arm, day 0 will be the day of randomization. For patients randomized to the MSC arm, day 0 will be the day of infusion. Patients in both treatment arms will be evaluated as follows:

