### **2.3.1 Primary endpoints:**

1. Treatment-related serious adverse events (tSAEs)
2. Improvement by at least two categories on a six category ordinal scale at day 14 post randomization. The six-category ordinal scale is as follows:  
6 = death; 5 = hospitalization, requiring extracorporeal membrane oxygenation (ECMO) and/or invasive mechanical ventilation (IMV); 4 = hospitalization, requiring non-invasive mechanical ventilation (NIV) and/or High-flow nasal cannula (HFNC) therapy; 3 = hospitalization, requiring supplemental oxygen (but not NIV/HFNC); 2 = hospitalization, not requiring supplemental oxygen; 1 = hospital discharge.

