### **5.3 Treatment Plan**

#### **5.3.1 Dosing**

Patients who are randomized to the MSC arm will be administered an intravenous infusion of MSCs at a dose of  $1 \times 10^8$ . A second infusion at the same dose will be allowed if the patient does not have improvement in respiratory parameters per discretion of the investigator, or ARDS clinically worsens, within 3-5 days following the initial infusion. When a patient is enrolled on the protocol a sufficient number of aliquoted cells will be thawed to provide the required cell dose. Thawing will be initiated on the planned date of administration according to the completed and signed Prescription for Administration received from the Principle Investigator on the study or designee. The thawed cells will be pooled, washed and formulated to the required final dose for administration. The release tests will be performed on the pooled cells prior to administration.

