## **8 Statistical Considerations**

### **8.1 Clinical Trial Design**

This is a single-center, open label, non-blinded randomized controlled, parallel study designed to evaluate the safety and clinical benefits of banked, allogeneic bone marrow MSCs versus control (routine supportive care) for treatment of COVID-19 related ARDS. The primary safety endpoint will be treatment-related serious adverse events (tSAE), defined in Section 7.4.5. The primary efficacy endpoint will be improvement in clinical status by at least two categories at day 14 post randomization, assessed by a six-category ordinal scale. The study will first enroll and treat 6 patients with MSCs for safety run in, then additional 60 patients will be randomized to receive either MSCs or supportive care designated by their treating physician.

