### **8.2 Sample size**

This early phase study will accrue a total of 66 patients with 6 patients for safety run in and additional 30 patients in each treatment arm by randomization. MSCs will be manufactured in our GMP facility and available to treat at least 36 patients. The study primary efficacy endpoint is improvement in clinical status at least two categories on a six-category ordinal scale at day 14 post randomization. The six-category ordinal scale ranges from 6 to 1 with a higher score indicates worse clinical outcome, i.e. 6 = death; 5 = hospitalization, requiring ECMO and/or IMV; 4 = hospitalization, requiring NIV and/or HFNC therapy; 3 = hospitalization, requiring supplemental oxygen (but not NIV/HFNC); 2 = hospitalization, not requiring supplemental oxygen; 1 = hospital discharge. The scale will be used to evaluate patients' status daily from baseline to day hospital discharge. Patients' clinical status at day 14 post randomization will be dichotomized as 'improved' (decreased by at least two categories) or 'not improved'. Patients who died before day 14 will be deemed as 'not improved'. Public data about the novel COVID-19 are limited and the data varies between all studies. Based on reported data, the time to improvement in patients with supportive care were about 22-23 days [20, 82] we expect 10% patients in the control group and 35%

patients in the MSC group will achieve 'improved' status at day 14, a total sample size of 66 (36 in the MSC arm and 30 in the control arm) will provide 84% power to detect a difference in clinical improvement of 25% between control (10%) and MSC (35%) at a 7.5% one-sided significance level using a Chi-square test.

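### Section 7 starts the clock at infusion in the MSC arm and at randomization in the control arm, which conflicts with the day-14-post-randomization primary endpoint and leaves the day-14 and day-28 secondary endpoints on arm-specific clocks

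*Combined protocol and SAP*

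**What the plan says.** Section 7 gives the only definition of day 0 in the document, and it differs by arm: "For patients randomized to the control arm, day 0 will be the day of randomization", and "For patients randomized to the MSC arm, day 0 will be the day of infusion".

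The primary efficacy endpoint counts from randomization in both arms, and the plan says so three times:
- Section 2.3.1: "Improvement by at least two categories on a six category ordinal scale at day 14 post randomization".
- Section 8.1: "improvement in clinical status by at least two categories at day 14 post randomization, assessed by a six-category ordinal scale".
- Section 8.2: "clinical status at day 14 post randomization will be dichotomized as" improved or not improved. Deaths before day 14 count as not improved.

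Other places bear on the clock:
- Section 2.3.2 lists endpoints at day 14 (ARDS severity) and day 28 (ordinal status, oxygenation-, ventilation- and ICU-free days, all-cause mortality) without naming an origin.
- Section 8.5 compares improvement at day 14 and day 28, again without an origin. It starts overall survival at randomization. Its ITT set is all eligible randomized subjects, infused or not.
- Section 6.1 marks both randomization and the first entry in the row "MSC Infusion for MSC arm" on Day 0.
- Section 5.3.1 ties preparation to the administration date, not to randomization: "Thawing will be initiated on the planned date of administration", and "The release tests will be performed on the pooled cells prior to administration".
- Section 7.2 has the ordinal scale scored daily until discharge or death, but ARDS severity only weekly after day 7.

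**The concern.** The two clocks agree only if every MSC patient is infused on the day of randomization. The calendar points that way, but no section requires it or sets a longest permitted interval. The separate sentence for the MSC arm in Section 7 does some work only when the two dates differ.

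When they do differ, a programmer building the Section 8.5 analysis from the calendar's Day 14 and Day 28 columns would observe MSC patients later after randomization than controls. In a population where some patients are recovering, later observation means more patients classed as improved, with or without a treatment effect. For all-cause mortality at day 28 the longer window works the other way and counts more MSC deaths. Mortality would also sit on two clocks, since overall survival runs from randomization.

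A patient randomized to MSC who is never infused belongs to the ITT set but has no day 0. That patient therefore has no origin for scheduled visits or for the day-14 and day-28 secondary endpoints. The trial is open-label and infusion follows a prescription from the investigator or a designee, so unblinded staff can influence the length of the gap.

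**Working it through.** **1. The plan's own figure.** Section 8.2 states 84% power for 10% v 35% improved, 30 control and 36 MSC, one-sided 7.5%, Chi-square test.
- Pooled rate = (30×0.10 + 36×0.35)/66 = 0.2364.
- SE under the null = √[0.2364×0.7636×(1/30 + 1/36)] = 0.1050.
- SE under the alternative = √[0.10×0.90/30 + 0.35×0.65/36] = 0.0965.
- Power = Φ[(0.25 − 1.4395×0.1050)/0.0965] = Φ(1.024) = 84.7%. The stated figure reproduces.

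The 36 includes six run-in patients who are not randomized. For the 30 v 30 randomized patients the same formula gives 82.2%. The checks below use 30 v 30.

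**2. Level with no lag.** I enumerated all outcomes of two binomials (30 each, both at 10%) and rejected when the pooled z exceeded 1.4395. The exact one-sided level is 6.9% against the nominal 7.5%.

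**3. Effect of a lag with no treatment effect.** The documents give no randomization-to-infusion interval, so 1, 2 and 3 days are assumptions, applied to every MSC patient. Controls are read at 14 days after randomization and MSC patients at 14 + lag. Two curves for time to improvement F(t) are used, both passing through the plan's 10% at day 14:
- *Constant hazard:* F(t) = 1 − exp(−ht), with h = −ln(0.90)/14 = 0.00753 per day.
- *Steep Weibull:* F(t) = 1 − exp[−(t/λ)^k], also passing through 50% at day 22.5. Then k = ln[ln 2/(−ln 0.90)]/ln(22.5/14) = 3.97 and λ = 22.5/(ln 2)^(1/k) = 24.7 days. The 22.5 is the midpoint of the 22–23 days in Section 8.2. Treating it as a median is an assumption, because the plan does not call it one.

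| Assumed lag (days) | Constant hazard: MSC improved | False-positive rate | Weibull: MSC improved | False-positive rate |
|---|---|---|---|---|
| 0 | 10.0% | 6.9% | 10.0% | 6.9% |
| 1 | 10.7% | 8.2% | 12.9% | 13.3% |
| 2 | 11.3% | 9.5% | 16.4% | 23.6% |
| 3 | 12.0% | 11.0% | 20.4% | 37.6% |

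**4. With one clock.** If randomization is day 0 in both arms, a lag adds no follow-up. The zero-lag row applies whatever the infusion date, and neither the sample size nor the planned power changes.

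**5. What can be re-derived later.** Daily scoring, together with the discharge and death categories, lets status at day 14 after randomization be obtained for each randomized patient who remains in follow-up, infused or not. ARDS severity at day 14 cannot be recovered in this way, because after day 7 it is assessed only weekly.

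**The case against.** The strongest reply is that the primary endpoint is already anchored correctly. The plan places it after randomization three times, identically for both arms, while Section 7 only introduces an evaluation schedule. A reader might infer from Section 7 that the primary endpoint itself gives MSC patients extra recovery time. The documents do not support that reading. The bias needs both a delayed infusion and an analyst who takes day-14 status from the infusion-based visit.

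A reader might also infer that uninfused MSC patients lack a primary outcome, or that deaths before infusion disappear. That does not hold either. They are in the ITT set, are scored daily, and count as not improved if they die before day 14.

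The evidence for a lag is thin. The product is banked and frozen, thawing happens on the administration date, and the calendar puts randomization and first infusion on the same day. Thaw, wash and release testing do not by themselves show a delay of days.

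Nor does the shift always favour MSC: overall survival runs from randomization, and a longer window adds MSC deaths by day 28. The Weibull figures rest on an assumed median and shape, let every patient eventually improve, and ignore death as a competing event, although Section 1.3 cites ARDS mortality near 50%.

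All of this stands, and it limits the size and reach of the point. It does not remove the conflict. Section 8.5 gives no origin for its day-14 and day-28 comparisons, and the fixed-day secondary endpoints have no origin other than Section 7.

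**Conclusion.** The plan is inconsistent as written. Its only definition of day 0 differs by arm, conflicts with the primary endpoint's origin, and by default governs the day-14 and day-28 secondary endpoints. Whenever infusion falls after the randomization day, following the Section 7 calendar gives the two arms different follow-up. It leaves uninfused MSC patients without a visit origin in every case.

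The size is conditional. For the primary test, an assumed lag of 1 to 3 days in every MSC patient raises the false-positive rate from 6.9% to between 8.2% and 11.0% under a constant hazard. The 13% to 38% from the steep curve is an upper scenario, not an estimate from the plan. The inflation is zero if infusion is on the same day or if the post-randomization wording is followed. For 28-day mortality the shift goes against MSC, so a general claim that efficacy is biased toward MSC would go too far.

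**What to change.** In Section 7 and the Section 6.1 calendar:
- Define day 0 as the date of randomization in both arms for all efficacy and mortality endpoints.
- Take baseline as the last ordinal score before randomization.
- Read day-14 and day-28 status from the daily scores counted from randomization, for infused and uninfused patients alike.
- Keep a separate time-since-infusion clock in the MSC arm only for infusion-related safety windows and cytokine sampling.
- Add the origin explicitly to the endpoints in Section 2.3.2 and to the day-14 and day-28 comparisons in Section 8.5.

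The six run-in patients are not randomized and are outside the ITT set, so the text should state their origin separately.

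The cost is a few sentences and a calendar footnote. The ordinal scale needs no new data, and the sample size is unchanged. The downsides are a second clock to track in the MSC arm, and weekly assessments such as ARDS severity that must be scheduled from randomization.

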### 7.1 Baseline Pre-treatment Evaluation

- 7.1.1 History and physical (including vitals and oxygenation requirements)
- 7.1.2 SARS-CoV-2 RT-PCR testing
- 7.1.3 ARDS assessment
- 7.1.4 Complete Blood Count and differential (CBC)
- 7.1.5 Complete Metabolic Panel (CMP)
- 7.1.6 Coagulation studies: PT/aPTT, d-dimer, fibrinogen
- 7.1.7 Lactate Dehydrogenase (LDH)
- 7.1.8 C-Reactive Protein (CRP)
- 7.1.9 CXR and/or CT chest imaging
- 7.1.10 Urine or serum pregnancy test for females of childbearing potential
- 7.1.11 APACHE II score
- 7.1.12 Medical record review for concomitant medications
- 7.1.13 Clinical status assessed by the six-category ordinal scale (1 = discharged; 6 = death)

### 7.2 Post-randomization/treatment Evaluation

- 7.2.1. History and physical (including vitals and oxygenation requirements) daily during hospitalization
- 7.2.2 ARDS assessment daily day 0 through 7, then weekly until day 28 if remains intubated in the ICU or until extubated, whichever occurs first, and ABG data available
- 7.2.2. The following routine laboratory investigations will be obtained through day 7, then weekly until day 28 or hospital discharge, whichever comes first
  - CBC
  - CMP
- 7.2.3. PT/aPTT, d-dimer, fibrinogen, CRP and LDH will be collected from the medical record, if available, at timepoints noted in the study calendar.
- 7.2.4. CXR and/or CT chest imaging will be done at baseline, then as then as clinically indicated per treating physician discretion. Data will be collected from the medical record, if available, at timepoints noted in the study calendar.
- 7.2.5. SOFA/CURB-65 score day 0, and day 28, if patient remains in the ICU and ABG available per SOC (for SOFA calculation).
- 7.2.6. Research cytokine profile and labs day 0 pre-infusion, 3-4 hours post-infusion, day 1, 3, 5, 7, 14 and day 28 if remains hospitalized. Optional if patient has

been discharged.

- 7.2.7.** Medical record review for data collection on supportive interventions, including but not limited to:
- Respiratory support (high flow nasal canula, AirVO, proning, high frequency oscillatory ventilation (HFOV), etc.)
  - Pharmacologic interventions (corticosteroids, vasopressors, paralytics, pulmonary vasodilators, etc.)
- 7.2.8.** Medical record review for data collection on concurrent medications (such as antibiotics, antivirals, antihypertensives, anticoagulants), concurrent infections, and other end-organ damage daily through day 28 or hospital discharge, whichever occurs first
- 7.2.10.** Clinical status assessed by the six category ordinal scale daily until hospital discharge or death, whichever occurs first.

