### **1.3 ARDS due to COVID-19 Disease**

Angiotensin converting enzyme-2 receptor (ACE-2) has been identified as a primary host receptor for cell entry utilized by SARS-CoV-2 similar to SARS-CoV [15, 16]. ACE-2 is highly expressed in multiple organs including but not limited to the oral cavity, human airway epithelia, myocardial cells, and kidney proximal tubule cells, and high expression may increase susceptibility to viral damage. It has been reported that approximately 50% of patients with COVID-19 pneumonia will progress to ARDS [12, 13, 17], with mortality approaching 50% in various studies [10, 12, 13, 17, 18]. Risk factors for ARDS and increased mortality include age (older than 60 years), presence of comorbidities such as hypertension, diabetes, heart disease, COPD, immunocompromised states, elevated markers of inflammation and higher disease severity as evidenced by high APACHE II, SOFA, and CURB-65 scores [10, 18-21]. At present, no effective antiviral treatment or vaccine is available; however, multiple clinical trials are evaluating the safety and efficacy of pharmacologic agents.

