### **2.3.3 Exploratory endpoints**

1. Changes in inflammatory markers (CRP, IL-6, IL-10, TNF- $\alpha$ )
2. Negative SARS-CoV-2 RT-PCR by day 28 (if available)
3. Changes in blood safety laboratories (CBC with differential, electrolytes, renal indices, liver function studies, LDH, coagulation studies if available)
4. Corticosteroid use and duration
5. Changes in chest imaging
6. Evolution of other end-organ damage (hepatic, renal, cardiovascular)
7. Changes in disease severity score (SOFA, CURB-65)
8. Duration of vasopressor use

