### 8.5 Statistical Analysis

All patients who received any MSC infusions in the MSCs arm or supportive care in the control arm will be included in the safety analyses. All efficacy analysis will be based on the intent to treat (ITT) population, defined as eligible and randomized subjects.

Adverse event data and corresponding toxicity grades after treatment will be summarized descriptively by treatment arms. All adverse events, grades, and attributions

will be listed and tabulated. Toxicity information including the type, severity, time of onset, time of resolution, and the probable association with the study regimen will be tabulated and summarized by treatment arms. Rate of tSAEs in patients treated with MSCs will be reported as proportion and its 95% confidence interval overall and by cancer status (cancer patients versus non-oncologic patients).

Clinical outcome data (increase in oxygen saturation, decrease in oxygen supplementation, progression to mechanical ventilation or ECMO, evolution of other end-organ damage, severity of ARDS, mortality rate, cause of death, duration on ventilation, durations of ICU stay and hospital stay, duration of vasopressor use, negative SARS-Co-V-2 RT-PCR by day 28, and change in disease severity scores and corticosteroid use) will be summarized descriptively. Categorical variables will be summarized by frequencies and percentages. Continuous variables will be summarized by means, standard deviations, medians, interquartile ranges.

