Proportion of patients who have an improvement of at least two categories on a six category ordinal scale at day 14 and day 28 will be summarized using rate and their 95% confidence interval by treatment arms and compared with Chi-square tests. Proportion of patients with improvement will also be reported by cancer status. As exploratory analyses, improvement in clinical status will also be assessed using logistic regression, adjusting for potential confounders such as age, race/ethnicity, underlying condition, and severity of ARDS. Changes in the six-point ordinal scale, oxygen saturation, required FiO2, severity scores from baseline will be presented graphically and compared with paired t-tests or Wilcoxon signed rank tests, whichever are appropriate (comparisons are considered exploratory). Duration of overall survival will be days from date of randomization to date of death or date of last follow-up for censoring. Overall survival will be calculated using Kaplan-Meier survival curves with estimates of medians and 95% confidence intervals by each treatment arm and compared with a log-rank test (comparison is considered exploratory).

Laboratory data, which include inflammatory markers and chest imaging will be reported with appropriate summary statistics. Changes from baseline to post-treatment will be plotted for each patient over time and assessed using paired test methodologies when appropriate. Comparison between the two treatment groups will be exploratory with appropriate two-sample tests.

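### Change in SOFA/CURB-65 has one follow-up score, taken only in patients still in the ICU at day 28, so the planned change-from-baseline analysis of this exploratory endpoint is selected on outcome.

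*Combined protocol and SAP*

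**What the plan says.** Section 2.3.3 lists "Changes in disease severity score (SOFA, CURB-65") as exploratory endpoint 7. Section 7.2.5 sets the schedule: "SOFA/CURB-65 score day 0, and day 28, if patient remains in the ICU and ABG available per SOC (for SOFA calculation"). The calendar in 6.1 agrees on follow-up. Its joint SOFA/CURB-65 row has one post-baseline mark, at day 28, with a footnote limiting it to a patient "if remains in the ICU and ABG available per SOC".

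Section 8.5 lists "change in disease severity scores and corticosteroid use" among the outcomes to be summarised descriptively. It then says that "severity scores from baseline will be presented graphically and compared with paired t-tests or Wilcoxon signed rank tests", and labels these comparisons exploratory. It also says that efficacy analyses follow intention to treat.

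The only rule for deaths belongs to the dichotomised primary endpoint in section 8.2: "Patients who died before day 14 will be deemed as" not improved. No similar rule exists for SOFA or CURB-65, and none covers a patient who moved to the ward, was discharged or had no blood gas.

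The starting score is dated in two ways. The calendar marks the pre-treatment column and leaves day 0 empty. Section 7.2.5 says day 0, which section 7 defines as the day of randomisation for controls and the day of infusion for the MSC arm. The baseline list in 7.1 includes APACHE II but neither SOFA nor CURB-65.

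**The concern.** To have a change score, a patient must be alive at day 28, still in the ICU and, at least for SOFA, have had a blood gas. All three are states reached after randomisation, and treatment may alter each of them. The worst outcomes leave the analysis through death, and the best leave it through recovery.

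The distortion can go in either direction. If MSCs keep very ill patients alive in the ICU, those patients are scored in the MSC arm while comparable controls are lost as deaths. If MSCs speed recovery, the patients who benefited are the ones with no score. A paired test within an arm has the same problem, because it describes only those who neither died nor improved enough to leave the ICU. At stake is the interpretation of this one exploratory score.

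**Working it through.** The plan gives no figure for this analysis, so there is none to reproduce. Its only power statement concerns the day-14 primary endpoint and has no bearing here.

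**Step 1: who has a day-28 value under 7.2.5 and 6.1**

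| Status at day 28 | Score under the plan | Rule in 8.5 |
|---|---|---|
| Dead | None | None |
| Discharged | None | None |
| In hospital, outside the ICU | None | None |
| In the ICU, no blood gas | No SOFA; CURB-65 unclear | None |
| In the ICU, blood gas available | SOFA and CURB-65 | Paired change |

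**Step 2: how many that could be**

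Inputs:
- 30 randomised patients per arm (section 8.2).
- Mortality 30-50%. Section 1.3 describes COVID-19 ARDS "with mortality approaching 50% in various studies", without a day-28 horizon; the lower end is assumed.
- Share of survivors still in the ICU at day 28: 10-50% (assumed; not in the documents).
- Share of those with a blood gas: 70-100% (assumed; not in the documents).

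Scored per arm = 30 × (1 − mortality) × share in ICU × share with blood gas.

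- Low: 30 × 0.50 × 0.10 × 0.70 = 1.05
- Middle: 30 × 0.60 × 0.30 × 1.00 = 5.4
- High: 30 × 0.70 × 0.50 × 1.00 = 10.5

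This is about 1 to 10 of 30 per arm, or 3.5% to 35%. At 50% mortality the ceiling is 30 × 0.50 = 15, even if every survivor were still in the ICU with a blood gas. If the blood-gas condition does not apply to CURB-65, its low case rises only to 30 × 0.50 × 0.10 = 1.5 and its high case stays at 10.5. The ICU condition does most of the damage.

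**Step 3: what the selection can do**

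This illustration is built wholly on assumptions. Let each patient have a latent change in severity, normal with SD 1, higher being worse. Set the cut-offs so that in the control arm 40% die, 40% leave the ICU and 20% remain. Apply the same cut-offs to an MSC arm shifted by a true benefit of 0.5 SD. Simulated results:

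| | Control | MSC |
|---|---|---|
| Die | 40% | 22% |
| Leave the ICU | 40% | 60% |
| Remain and are scored | 20% | 18% |
| Mean change, all patients | 0.00 | −0.50 |
| Mean change, scored patients | 0.00 | −0.01 |

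A benefit large enough to nearly halve deaths disappears among the scored patients. The paired test in the MSC arm would be looking at a mean change of about zero.

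**The case against.** The strongest reply is that little depends on this endpoint. It is item 7 of 8 exploratory endpoints, and its comparisons are labelled exploratory. Deaths and recoveries are captured elsewhere: the day-28 ordinal scale, ICU-free and ventilation/ECMO-free days, time to discharge, overall survival and day-28 mortality. That stands in full. A reader might infer that a real benefit could appear as harm in the trial's main results. The documents do not support this, because no primary or secondary endpoint uses these scores.

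Second, section 8.5 names paired, within-patient tests for severity scores. Its explicit sentence on comparing the two groups sits in the paragraph on laboratory data and imaging. A standard error for a between-arm difference in mean SOFA would therefore measure an analysis that is not clearly planned, and none is offered here. Selection still affects the paired analysis.

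Third, a reader might infer that the plan requires a blood gas for CURB-65. The parenthesis in 7.2.5 can be read as tying the blood gas to SOFA alone, while the calendar footnote marks the joint row. This is ambiguous wording. Only the ICU condition clearly reaches CURB-65.

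Fourth, the documents give no ICU occupancy or blood-gas rate at day 28, so a small scored group is an inference. The selection itself does not depend on that number.

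**Conclusion.** The concern holds for this endpoint alone. As written, the plan produces a change-from-baseline result in patients picked out by their outcome, and that result could mask or distort a treatment effect on SOFA or CURB-65. It also cannot be run on all randomised patients, as the intention-to-treat statement in 8.5 would require. The estimate of about 1 to 10 scored patients per arm depends on the assumed ranges above. Only the mortality figure near 50% comes from the documents.

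The two dates for the starting score are a separate inconsistency to be reconciled. No effect of it on the result has been shown. This is a desirable improvement rather than a threat to the trial's conclusions.

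**What to change.** - **Sections 6.1 and 7.2.5, CURB-65.** Remove the ICU condition and state that the blood-gas condition applies to SOFA only. Derive CURB-65 at days 7, 14 and 28 for all hospitalised patients from the vital signs, examination, CMP and age already collected.
- **Sections 6.1 and 7.2.5, SOFA.** Derive it at the same days where a blood gas exists.
- **Baseline.** Reconcile the calendar, 7.1 and 7.2.5 to a pre-randomisation value in both arms.
- **Section 8.5, CURB-65.** Compare arms by ranks, with death worst and discharge alive best.
- **Section 8.5, SOFA.** Report change as descriptive among scored patients only, with counts by arm of dead, discharged and unscored. An all-patient rank test for SOFA would be incomplete, because patients alive in hospital without a blood gas have no rank.

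The cost is a few more chart-derived scores at visits already scheduled, plus wording. The CURB-65 result becomes a rank comparison instead of a change in points and partly overlaps the day-28 ordinal scale. SOFA remains selected on blood-gas availability, which is why it should stay descriptive.
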